- iv. There is no significant difference in means between the pre-test among the newly employed nurses (NEN) among interventional and the control groups in all dependent variables.
- v. There is a significant mean difference between PRE-SBLST and all POST-SBLST results among NEN in all dependent variables.

Study Design

The study design was a prospective, longitudinal, single-blind basic experimental design, randomized control trial (RCT) design.

Study Location

The study was carried out in Jordan; Amman and Al-Zarqa City. The accessible population was NEN in five hospitals. The researchers selected three Jordanian hospitals. The selection was according to the capacity, capability of the institution and eligibility criteria. Computer-generated randomization (Random Allocation Software, version 1.0) was applied in blocks to allocate the hospitals by distributing them into two arms. The first arm was the control group; selected from three hospitals; Prince Hamza Hospital, AL-Basheer Hospital, and AL-Zarqa Governmental Hospital (n=51); the second arm was the interventional group from two hospitals; Prince Faisal Governmental Hospital and Dr.Jameel AL-Totanji Hospital.

Randomization of the Hospitals

To prevent data contamination between the control and interventional groups, computer-generated randomization (Random Allocation Software, version 1.0) was applied in blocks to allocate the hospitals by distributing them into two arms. The first arm was the control group; selected from three hospitals; Prince Hamza Hospital, AL-Basheer Hospital, and AL-Zarqa Governmental Hospital (n=51); the second arm was the interventional group from two hospitals; Prince Faisal governmental hospital and Dr.Jameel AL-Totajji hospital. The control and interventional groups were selected from different hospitals because the researchers are always worried about data contamination and try to minimize it between the control and intervention groups; if the sample was selected from the same area and both groups worked closely together, the data would be contaminated.

Inclusion Criteria

The researchers tried to maintain homogeneity and minimize any variations among the participants by

1. selecting both interventional and control groups from newly employed nurses
2. Male and female participants
3. Participants only who understand the questionnaires and interventions in English

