After NEN enrolled according to the inclusion criteria for both the control group and experimental group (n= 102), the participants started by signing the informed consent, filled out the demographical data and pre-test as proactive steps before the intervention; many sessions of pre-test data collection and intervention were performed according to the availability of NEN, the arrangement of the hospital's nursing director. The estimated time to fill in the demographical data and pre-test is around 30 minutes. Oermann et al. (2020) addressed that the trainer performs a pre-test assessment to assess the effectiveness of SBLST. The investigators discussed the purpose of the study with the control group and explained to them the procedure to prevent any data contamination and minimize the interpretation of the survey content with the other

Intervention

The control group read the brochure containing a brief guideline about basic life support for 30-60 minutes before taking the post-test. Standard treatment ran from Dec 2022 to Jan 2023. One full day for SBLST intervention, from 5 to 7 hours for SBLST intervention is required based on the recent research and uses AHA-2020 guidelines. The number of participants was ten NEN in each session. The

interventional treatment consists of theoretical and practical parts. The SBLST intervention was conducted in an educational lab according to the hospital's capability; SBLST ran for seven days, from 22 Nov 2022 to 20-Dec, 2022.

Researchers combined two frameworks in the SBLST. Miller's Pyramid and Kolb's Cycle; Miller's Pyramid focuses on teaching theoretical and practical aspects of the task through simulation and allowing trainees to perform the procedure independently with guidance; Kolb's Cycle suggests giving learners a scenario to practice until they eliminate errors before moving to another scenario. The SBLST intervention was reviewed by three experts in BLS and approved by the Jordanian Ministry of Health-Life Support Center. It was found to be compliant, safe and covered all aspects of AHA-2020. English experts provided feedback to improve clarity. A pilot study was conducted on 20 nurses to calculate SBLST time, identify errors, monitor the progress and calculate Cronbach's Alpha.

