Adult half-body manikin and a pediatric full-body manikin are necessary; with lung bag inflation and deflation characteristics, palpable carotid pulse, the chest includes spring inside to facilitate chest recoil, and chest compression board, bag-valve-mask-ventilation, chest compression performed on the Charlie simulator to relieve choking. The principles investigator (PI) had a master's degree in critical care nursing, eighteen years of experience between ICUs, lecturers and clinical instructors, valid BLS and ACLS, training of trainers in nursing education, and randomized control trial training. The facilitator must have CPR certifications in BLS and ACLS, enough expertise in education and training, and good communication skills the investigator had a master degree in critical care. Two research assistants supported the

PI in collecting data; one research assistant for the control group and the other for the interventional group.

Post-test

All participants completed the immediate post-test-1 after the interventions. The post-test-2 was conducted by providing the participants with a Google Form Platform link through their phone and email addresses. The post-test after three months evaluates whether the participants' level stayed at the same level or minimized by comparing the mean value between all post-tests. Forty-eight participants in the experimental group completed post-test-2 with a response rate of 94%, and 45 participants in the control group with a response rate of 88%.

Sample Size Estimation

Sample size calculation is performed by using G*POWER software (version 3.1); sample size calculation is summarized and consists of the following steps (1) Select the test family (F-test family), (2) Select the statistical test (Select ANOVA-repeated test, between factors), the preliminary test analysis the researchers used in this study, the rationale for using the Select ANOVA-repeated test between factors due to measure many dependent variables means at different time points. (3) The parameters selected to calculate sample size include one side tail, alpha (α) and equals (0.05)- type one error, Power (P) and equal (0.8), effect size, the number of groups is two (each group = $n/2$) n = the estimated sample size, number of measurements were four measurements (Pre-test, Post-test immediately, Post-test after two months, and Post-test after three months).

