Effect Size (ES) = 0.26, automatically calculated by G*Power software, depending on the sample size of the previous study, the effect size is calculated, the

Control group's post-test result $M \pm SD$ was equal (25.03 ± 3.04) with a sample size of 28 participants, and the interventional group (26.64 ± 2.64) with sample size 29 participants. The sample size is 72 participants; because the research study continued for three months, we added a 10% drop rate for each month, so the drop rate is 30%. Final sample size estimation including drop rate ($n \setminus (1 - \text{dropout rate}) = 72 / (1 - 0.30) = 102$ participants, the intervention group arm is 51 participants, and The largest sample size was obtained from the interventional group, more than the Control Group and the Control group arm 51 participants.

Simple Random Sampling of the Participants

After obtaining ethical approval and permission to conduct the study from the Ministry of Health in Jordan, approval letter (Education/Info\ 15177) and ethical approval letter (MOH/REC/2022/340), The researchers started the formal face-to-face visits to arrange with the nursing director and a continuous education office in the selected hospitals about the study objective and how the study would proceed; The researchers received the activation letter to initiate the study and prepared the list of the available participants who met the study's eligibility criteria. The number of participants depends on the availability of newly employed nurses in the institution who meet the inclusion criteria. The researchers randomly selected the participants from the participants' list by randomly sampling from newly employed nurses in each hospital for interventional and control groups.

. The response of the control group hospitals was as the following; the nursing director and continuous education in AL-Zarqa Governmental Hospital responded by providing all the information about participants and selecting a time and day to perform the Pre-test, standard treatment and the immediate post-test. Prince Hamzah Hospital and AL-Basheer Hospital gave the researcher the names of departments in the

hospital, including those with NEN, and we visited these departments to select the available NEN randomly and performed Pre-test, standard treatment, and immediate post-test in their departments.

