DEVELOPMENT, VALIDATION, AND
EVALUATION OF THE EFFECTIVENESS OF
SIMULATION IN BASIC LIFE SUPPORT TRAINING
(SBLST) ON NEWLY EMPLOYED NURSES IN
GOVERNMENTAL JORDANIAN HOSPITALS

Statistical Analysis Plan

Last update On 20-4-2023

Malaysian Human subjects protection review board date: 20-4-2023

Statistical Analysis Plan

Introduction

The data will be collected through the Google Forms platform, and the researchers will extract the data responses from Google Forms as an Excel sheet (Microsoft Office 2016); all the quantitative data will be coded and transferred to IBM SPSS version 27; the data will be analyzed by using (1) descriptive and (2) inferential statistic.

1. Descriptive Statistics

The descriptive statistic will illustrate the homogeneity and characteristics of NEN in the control and experimental group, including the number and percentage of participants for each group. Also, it will be used to describe statistics for participants' knowledge, practice and confidence level mean percentage in the pre-test and post-test scores.

2. Inferential Statistics

A. Independent T-test

Independent T-test will be used to identify the homogeneity or heterogeneity between pre-tests and post-tests in the control and experimental groups in all dependent variables by interpreting the *P*-value and comparing means (SD). The researchers plan to use independent T-tests despite the normality assumption not being fulfilled depending on the central limit theorem, which states that if samples are more than 30 participants in each group, the researcher can use mean and SD.

B. Repeated Measures-ANOVA

The researchers will use "Repeated Measurement ANOVA" for inferential statistics of the mean of the dependent variables between the interventional and comparator groups in all pre-test and post-tests. Finally, the researchers compared the

*

“Mean,” “Standard Deviation,” and significant level (*P*-value) between tests to explore the effectiveness of the intervention SBLST.

In this step of the analysis, the researchers want to estimate a good idea about the outcomes and how SBLST is considered a good intervention or not after comparing the knowledge score, practice score, and confidence level in both interventional and control groups. The researchers selected a *P*-value < 0.05 for statistical analysis significant to accept the alternative hypothesis or reject the null hypothesis.

C. Effect Size (Cohen’s Score)

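### Whole hospitals were allocated (three control, two SBLST), but the sample size and the planned tests treat the nurses as independent

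*Protocol*

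**What the plan says.** **Allocation.** The protocol's Study Location section states: "Computer-generated randomization (Random Allocation Software, version 1.0) was applied in blocks to allocate the hospitals by distributing them into two arms". The Randomization of the Hospitals section repeats this. Both list three control hospitals (n=51) and two interventional hospitals, and the second explains that the arms were kept in separate hospitals to avoid contamination. Study Location also contains an inconsistency about the number of hospitals: "The accessible population was NEN in five hospitals. The researchers selected three Jordanian hospitals". Five are then named, and this point uses those five.

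**Selection of nurses.** Under Simple Random Sampling of the Participants, nurses are drawn at random from lists within hospitals whose arm is already fixed. Hospital sizes were not set in advance: "The number of participants depends on the availability of newly employed nurses in the institution who meet the inclusion criteria".

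**Sample size.** The Sample Size Estimation section uses G*Power for individuals: "2) Select the statistical test (Select ANOVA-repeated test, between factors". It takes f = 0.26, alpha 0.05, power 0.80, two groups and four measurements. This gives 72, raised to 102 (51 per arm) for 30% dropout. No ICC, design effect or number of clusters appears.

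**Analysis.** SAP section 2.A: "Independent T-test will be used to identify the homogeneity or heterogeneity between pre-tests and post-tests in the control and experimental groups". SAP section 2.B plans repeated-measures ANOVA "for inferential statistics of the mean of the dependent variables between the interventional and comparator groups in all pre-test and post-tests". Significance is P < 0.05. Neither section includes hospital, and 2.B does not say whether the group effect or the group-by-time effect is the test.

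**The concern.** No hospital contributes nurses to both arms, so any difference between hospitals is mixed with the difference between arms. The random draw of nurses within hospitals is sampling. It does not allocate nurses to treatment and does not remove this problem.

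Tests that count 102 independent nurses understate the uncertainty when nurses in one hospital resemble each other. The tests exposed are those the protocol relies on: its Objective section predicts between-arm differences in post-test scores, and the power calculation is for the between-factors (averaged group) effect. The pre-test t-tests for hypothesis iv have the same defect. SBLST could be declared effective because of hospital differences.

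A stable hospital difference cancels from the group-by-time contrast. That contrast is affected only if hospitals differ in how scores change. This is possible, because conditions varied by site. "The SBLST intervention was conducted in an educational lab according to the hospital's capability", says the Intervention section. Two control hospitals "performed Pre-test, standard treatment, and immediate post-test in their departments", while the third scheduled a day and time for its nurses.

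**Working it through.** **1. The plan's own figure.** From the previous study quoted in the protocol, the mean difference is 26.64 - 25.03 = 1.61. With the control SD of 3.04, f = 1.61/(2 x 3.04) = 0.2648, printed as 0.26. For the between-factors test, lambda = f² x N x m/(1 + (m-1) x rho). The protocol gives no within-person correlation rho; 0.5 is assumed.

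- f = 0.2648, N = 72, m = 4: lambda = 8.08, power 0.800. This reproduces the stated 72.
- Dropout: 72/0.70 = 102.9, against 102 stated.

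So the figure reproduces as an individual-level calculation with no allowance for clustering.

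**2. Design effect for one test.** Assumed hospital sizes are 17/17/17 (control) and 26/25 (SBLST). With total variance 1, the variance of the difference in arm means is

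ICC x (1/3 + 0.5002) + 2(1 - ICC)/51, against 2/51 = 0.0392 without clustering.

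The approximate type I error of the naive test is 2 x [1 - Phi(1.96/sqrt(DE))], where DE is the ratio of the two variances. Simulation (40,000 runs) gives slightly higher values at large ICC.

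| ICC | Design effect | Formula | Simulated |
|---|---|---|---|
| 0.01 | 1.203 | 0.074 | 0.074 |
| 0.02 | 1.405 | 0.098 | 0.102 |
| 0.05 | 2.013 | 0.167 | 0.173 |
| 0.10 | 3.025 | 0.260 | 0.263 |

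At ICC 0.001 the formula gives 0.052. With an uneven split of 31/10/10 and 36/15, the simulated rates at the four tabled ICCs are 8%, 11%, 19% and 31%.

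**3. Averaged group effect (three tests, rho 0.5).** Averaging shrinks the nurse-level noise but not the hospital effect. The variance of a nurse's mean of three tests is (1 + 2 x 0.5)/3 = 2/3, so the hospital share rises from ICC to ICC/(2/3). Simulated type I error is 0.086, 0.124, 0.222 and 0.342 at the same four ICCs.

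**4. Group-by-time.** With a stable hospital effect, the naive test of change from pre-test to post-test-2 stays at 0.050 to 0.051 at every ICC. With stable ICC 0.02 and hospital-by-time variance of 0, 1%, 2% and 5% of total variance, the group-by-time F test rejects in 0.049, 0.120, 0.193 and 0.380 of trials.

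**5. Power of the planned test at N = 102.** lambda = 0.26² x 102 x 4/2.5 = 11.03 on 1 and 100 df, power 0.908 with no clustering. Dividing lambda by the design effect (ICC taken for a nurse's averaged score) gives the second column. The third column is a noncentral t test on hospital means with 5 - 2 = 3 df.

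| ICC | Design effect only | Hospital-level, 3 df |
|---|---|---|
| 0 | 0.908 | 0.611 |
| 0.01 | 0.851 | 0.540 |
| 0.02 | 0.792 | 0.483 |
| 0.05 | 0.640 | 0.369 |
| 0.10 | 0.473 | 0.269 |

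If the ICC applies to each single test instead, the columns become 82%, 73%, 53%, 36% and 51%, 43%, 30%, 21% for ICC 0.01 to 0.10. With three measurements, as the study actually has, unclustered power is 0.890 and the design-effect column falls to 83%, 77%, 61% and 45%.

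**6. A valid alternative.** A pooled t-test on the five hospital mean changes keeps its type I error (0.045 to 0.048 simulated). With rho 0.5, a change score has variance 1 + 1 - 2 x 0.5 = 1, so the difference is 0.52 SD (2 x 0.26). Simulated power is 41% with no hospital-by-time variance and 32% if that variance is 1%.

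**The case against.** **The ICC is unknown and may be small.** Eligibility is narrow: newly employed nurses from one pandemic cohort, no ICU staff, no recent BLS training. They had little time to acquire hospital-specific skill. At ICC 0.001 the inflation is trivial. This stands as a limit on the size of the problem. It does not show that the ICC is negligible, and it says nothing about differences in delivery.

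**Hospital-by-time variance is conjecture.** The two phrases on site conditions describe the training lab and the place of testing, not different SBLST content. That is fair. The group-by-time figures are conditional, and no inflation is claimed there for a stable hospital effect.

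**The power comparison starts too high.** The 80% belongs to N = 72, and 102 includes a dropout allowance. The calculation also assumes four measurements where the study has three, which moves power by two to three points. Both remarks are correct. They concern the power statement, not the validity of the tests.

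**The remedy is weak with five hospitals.** There are only 10 ways to choose two hospitals of five, so a hospital-level permutation p-value cannot fall below 0.10, and the 3-df t-test leans on normality of five means. A mixed model is fragile: in a simplified simulation with one hospital variance, the estimate was zero in 45 to 60% of runs at ICC 0 to 0.02. This stands and should be stated. It is a limit of the design, and the nurse-level analysis conceals it.

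**Conclusion.** The concern holds and must be fixed. The unit of allocation is the hospital, and neither the sample size nor the SAP acknowledges it. For any positive ICC, the between-arm t-tests and the averaged group effect do not have a 5% error rate. Over ICCs of 0.01 to 0.10, the post-test t-test runs at about 7% to 26% and the averaged effect at about 9% to 34%. Group-by-time is affected only if hospitals differ in change.

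The direction follows from the documents alone. The size rests on an assumed ICC, within-person correlation of 0.5 and assumed hospital sizes. The power figures matter less: they show that the 80% statement carries no allowance for clustering.

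**What to change.** - Describe the trial as cluster-randomised with three control and two SBLST hospitals, and reconcile the five and three in Study Location.
- State which contrast is the test of SBLST.
- Base between-arm inference on a t-test with 3 df, using either the five hospital mean changes or hospital means adjusted for pre-test at nurse level. A mixed model with nurse, hospital and hospital-by-time random effects and small-sample degrees of freedom is an alternative, with the caution that five hospitals estimate those variances poorly.
- Report the ICC for each outcome, and say plainly how little three versus two hospitals can support.
- Replace the unqualified 80% power with power over an ICC range such as 0.01 to 0.10. No extra enrolment is proposed.

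**Cost.** Wording changes in both documents and a re-analysis by hospital. First confirm that each record can be linked to its hospital. Recruitment ran hospital by hospital, so this should be recoverable, but the demographic section does not list hospital, and the privacy section mentions only phone number and email as identifiers. Intervals will be wider and stated power lower, so a non-significant hospital-level result would say little about whether SBLST works.

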DEVELOPMENT, VALIDATION, AND
EVALUATION OF THE EFFECTIVENESS OF
SIMULATION IN BASIC LIFE SUPPORT TRAINING
(SBLST), ON NEWLY EMPLOYED NURSES IN
GOVERNMENTAL JORDANIAN HOSPITALS

Study Protocol

Last update On 20-4-2023

Malaysian Human subjects protection review board date: 20-4-2023

Study title:
DEVELOPMENT, VALIDATION, AND EVALUATION OF THE
EFFECTIVENESS OF SIMULATION IN BASIC LIFE SUPPORT TRAINING
(SBLST) ON NEWLY EMPLOYED NURSES IN GOVERNMENTAL
JORDANIAN HOSPITALS

Objective

The general objective of this study is to develop, validate and evaluate the effectiveness of simulation in basic life support training (SBLST) among newly employed nurses in Jordanian governmental hospitals; the study design is a basic experimental study design, randomized control trial (RCT) design, the dependant variables measure in this study; knowledge, practice and confidence by using a pre-test and two follow up tests, two groups are participating in this study; experimental and control group. The control group treatment is the standard intervention (brochure), and the experimental group intervention is a simulation in basic life support training (SBLST); researchers' hypothesized that there are no significant differences between the control and experimental group in the inclusion criteria and pre-test score; furthermore, the simulation in basic life support training intervention significantly improves knowledge, practice and confidence level among newly employed nurses (NEN) in Jordanian governmental hospitals; moreover, there is a significant difference between control and experimental group in the post-test scores in all dependant variables. The study process includes four steps

- Perform the pre-test (assess knowledge, practice confidence surveys)
- Education intervention knowledge and practice
- Perform the post-test 1 (assess knowledge, practice confidence surveys)
- Perform post-test 2 (assess knowledge, practice confidence surveys)

Research Hypotheses

- i. The simulation in basic life support training intervention effectively improves knowledge among newly employed nurses (NEN) in Jordanian governmental hospitals.
- ii. The simulation in basic life support training intervention effectively improves practice among newly employed nurses (NEN) in Jordanian governmental hospitals.
- iii. The simulation in basic life support training intervention effectively improves the confidence level among newly employed nurses (NEN) in Jordanian governmental hospitals.

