4. Participants who were previously on-seat undergraduate nursing students last two years, 2020 (4th year nursing bachelor level) and 2021 (3rd year nursing bachelor level) in the period of COVID-19 pandemic and receive basic and clinical learning by online method, and now became a newly employed nurse (NEN) in hospitals and delivered care to the patient.
5. Participants can attend five to seven hours of SBLST session.
6. For more control, we selected nurses who rarely face CPR and do not attend BLS raining the last two years.

Exclusion Criteria

1. The researchers excluded the NEN participants working in intensive care units because ICU nurses face CPR and perform BLS daily.
2. Excluded participants with medical or physical health problems (e.g., pregnant women and participants complaining of lower back pain).
3. Participants who attended CPR training less than two years previously were also excluded. Finally,
4. NEN who upgraded their educational degree from a diploma to a bachelor's degree were excluded.

Research Instruments

The study consists of a pre-test, intervention, immediate post-test-1 after the intervention, and finally, the post-test-2 three months after the intervention. This study measured knowledge, practice, and confidence through pre- and post-tests in control and experimental groups. This study used two interventions: SBLST for the interventional group and AHA-BLS 2020 brochure as a standard treatment for the control group. Data collection proceeded using the Google Form Platform (A web-based instrument Copyrighted by Google application).

The evaluation process includes a pre-test and two follow-up assessments to measure knowledge, practice and confidence. The researcher will analyse the means of each test; the total dependent variables were 30 questions listed in.

Languages of the Tools

According to the HCP educational level, all four sections of the tools assessment are written in English; furthermore, the researchers' assistance clarified any misunderstanding points or need for translation to the participants.

Tools Sections

The tools consist of five sections; research information sheet and consent forms, demographical data, knowledge assessment tools, skills assessment tools, and confidence level assessment tools.

Research information sheet and Consent Forms

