The research information sheet is a piece of brief researcher information and contact details; it also includes subject information and a consent form with an area for the participant's signature when they are approved to participate in this study. Furthermore, the research information sheets include a participant's publication consent form.

Demographical data

Demographic parts are attached in; these data consist of dichotomous questions (Yes\NO), nominal data, ordinal data, and interval measurement questions. Nominal measurements include sex and ordinal assessment as educational level and area of experience; interval assessment questions include age and work experience. Dichotomous assessments (Yes\NO), asking if the participant previously participated in a CPR episode or observed any CPR before, if the participants had finished training the BLS using simulation previously, and if the participant gained the certification of BLS training from formal and accredited institutions previously.

Knowledge and practice

Nursing knowledge is the interaction of science and research to improve practice. Researchers use a 13-question MCQ tool to assess knowledge. Nursing practice is performing the knowledge learned before; the researchers assessed skills using a tool consisting of ten MCQ. The participants got zero for each wrong answer and one mark for each correct answer.

Confidence

Confidence is the build and accomplishment of the nursing profession through knowledge acquisition, skills, and critical thinking. Confidence is the positive feeling of faith and dependability to perform BLS without fear and free from risk to the patient. The researchers assessed confidence level using seven statements rated as a dropdown in percent value from the lowest value of 5% to the highest value of 100%.

Study Process

Pre-test

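### The practice outcome is a ten-item written MCQ score with no observed BLS performance, so hypothesis ii should be concluded on that written score only

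*Protocol*

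**What the plan says.** The Knowledge and practice section of the protocol gives a definition and a measure in the same sentence. The definition is "Nursing practice is performing the knowledge learned before". The measure follows at once: "the researchers assessed skills using a tool consisting of ten MCQ". Scoring is binary: "The participants got zero for each wrong answer and one mark for each correct answer".

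The other two outcomes are described nearby. For knowledge, "Researchers use a 13-question MCQ tool to assess knowledge". For confidence, "The researchers assessed confidence level using seven statements rated as a dropdown in percent value". Research Instruments gives the size of the whole outcome set, "the total dependent variables were 30 questions", and the mode of collection, "Data collection proceeded using the Google Form Platform". The Post-test section adds that the three-month test reached participants as a form link sent by phone and email.

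The claims are worded more broadly. Hypothesis ii states that the training "effectively improves practice among newly employed nurses (NEN". Tools Sections lists the instrument among the assessments of skills. Community Sensitivities and Benefits expects the findings to raise nurses' practical skills. The SAP (Repeated Measures-ANOVA; Effect Size) judges effectiveness on the knowledge, practice and confidence scores and does not say that the practice score is a written one.

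**The concern.** The protocol sets its own standard for practice, which is performing, and then measures something else, which is choosing written answers. No outside standard is needed to see the gap.

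The gap matters because the intervention is hands-on. Compressions, bag-mask ventilation and relief of choking are trained on manikins and a simulator, so a reader told that practice improved will take this to mean that nurses carried out BLS better. Of the three effectiveness claims, this one lies closest to patients. If the plan is followed as written, a rise in a ten-item written score could be reported as a gain in performed BLS, and nothing in the SAP would prevent it.

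**Working it through.** **Step 1. Count the outcome items.** All inputs are from the protocol.

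| Outcome | Section | Items | Response | Observed performance |
|---|---|---|---|---|
| Knowledge | Knowledge and practice | 13 | MCQ, 0/1 | 0 |
| Practice | Knowledge and practice | 10 | MCQ, 0/1 | 0 |
| Confidence | Confidence | 7 | Self-rating, 5% to 100% | 0 |
| Sum | | 30 | | 0 |

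13 + 10 + 7 = 30, which reproduces the total stated in Research Instruments. The three instruments fill the outcome set, leaving no room for a separate performance measure.

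**Step 2. Range of the practice score.** Ten items at 0 or 1 give a minimum of 10 × 0 = 0 and a maximum of 10 × 1 = 10. The score is a count of correct written answers.

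**Step 3. Look for observed performance elsewhere.** The manikins and simulator, and the practice of scenarios until errors are eliminated, appear in the Intervention section as parts of the training. Neither document names a checklist, a rater or a manikin measurement as an outcome. Collection is by web form, and the three-month test was sent as a link.

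**Step 4. Look for a bridge from the written score to performance.** The Intervention section reports expert review of the training and a pilot in 20 nurses that included Cronbach's alpha. Alpha describes how consistently items hang together. It does not show that the score tracks what a nurse does on a manikin. No comparison of the MCQ with observed performance is described.

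**Step 5. Set the claim beside the measure.**

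| Question | Can the planned data answer it? |
|---|---|
| Do the arms differ on the ten-item written score? | Yes |
| Do nurses perform BLS better (practice as the protocol defines it)? | Not from these data alone |

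Hypothesis ii uses the word that the protocol defines by the second question, while the data address the first.

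**The case against.** The strongest reply is that the measure is disclosed. The protocol says openly that the tool is ten MCQ marked 0/1, hypothesis ii can be tested on that score, and the SAP speaks mostly of scores. A written test as a proxy is a design choice, and relabelling it changes no data, test or P-value. The skills wording under Community Sensitivities and Benefits describes expected benefits and is not an analysis conclusion. Renaming an outcome after collection also weakens traceability, and collection appears complete, since three-month response rates are already reported.

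Much of this stands. The score is comparable between arms, so the issue is the reach of the conclusion. Traceability is a good reason to keep the word practice in the outcome's name. Disclosure in one section does not settle the matter, though, because hypothesis ii, Tools Sections and the SAP use practice or skills without that qualification. The P-value stays the same, but the sentence it supports does not.

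Three stronger readings are tempting, and the documents do not support them:

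- **That hypothesis ii cannot be answered at all.** It can be tested on the written score; what fails is the step from that score to performing.
- **That all 23 MCQ (13 + 10) measure the same knowledge.** The shared format is stated, but the item texts are in an attachment not available here. The ten items might be recall, ordering of steps or scenario decisions.
- **That the plan counts practice as independent confirmation of knowledge.** Each outcome has its own hypothesis, and neither document calls one corroboration of the other.

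**Conclusion.** The point holds in this form: the practice outcome is a 0–10 written score, no observed BLS performance is measured, and under the protocol's own definition a difference on that score does not support a claim of improved practice or the skills label.

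Its size is one of the three effectiveness hypotheses (i to iii). All 10 practice items are MCQ, and 0 of the 30 outcome items are observed. The effect is on what may be concluded; no estimate, test or sample size moves.

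The conclusion rests on the stated format, marking, mode of collection and item total. It does not depend on the content of the ten items, because no content turns a multiple-choice web form into observed performance. It would soften if evidence existed that this MCQ tracks performed BLS; neither document describes any.

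**What to change.** 1. In the instruments section, hypothesis ii and the SAP, identify the outcome as a practice score (10-item written MCQ). Keeping the word practice lets the outcome be traced to the name under which it was collected. Hypotheses iv and v use the same variable and can rely on this definition.
2. In Tools Sections, replace or qualify the skills label in the same way.
3. In the SAP, state that the conclusion on hypothesis ii is restricted to the written score and that no conclusion on performed BLS skill will be drawn.

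The cost is a few lines of wording and a narrower claim. The data, tests and sample size stay as they are, and no new skills test is required.
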